#### 8.1.2 Secondary Effectiveness Endpoint Analyses

The hypotheses for the secondary endpoints are:

1. The Informity tool will identify DBS parameters that improve motor symptom scores compared to baseline
2. The Informity tool will identify DBS parameters that improve quality of life measurements compared to baseline.

The time required for programming with the Informity tool is shorter than that of the most recent programming session prior to enrollment.

## Clinical Investigation Plan

For the change in motor symptom scores, a repeated measure analysis of variance (RMANOVA) will be conducted to determine statistical differences from baseline. Post-hoc Tukey's pairwise comparisons will follow to determine specific differences between follow-up visits. The change in quality of life measurement will also be analyzed using a RMANOVA followed by Tukey's pairwise comparisons. A comparison of the duration of programming will be performed for the programming session preceding enrollment, and the Informity programming session with the Informity tool, using a paired t-test. All statistical analyses will be conducted assuming a type-1 error rate of 0.05 unless specifically stated otherwise.

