## Clinical Investigation Plan

### 4.2 Secondary Endpoints

- 1) Change in UPDRS III for PD subjects or Fahn-Tolosa-Marin tremor rating scale for ET subjects at 3- and 6-month follow-up visits compared to baseline
- 2) Change in quality of life measurement as measured by the PDQ-39 for PD subjects or QUEST for ET subjects at the 3- and 6-month follow-up visits compared to baseline
- 3) Duration of programming at the Informity programming visit compared to the most recent programming session prior to enrollment
- 4) Change in TEED at the 3- and 6-month follow-up visits compared to baseline

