### 8.4 Multiplicity

All statistical tests will be performed with a type-1 error rate 0.05, unless otherwise stated. Family-wise error for RMANOVA will be addressed using Tukey's pairwise post-hoc comparisons.

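### Tukey all-pairs comparisons adjust for a 3- versus 6-month pair that no endpoint asks for, and the plan does not say how non-sphericity is handled in the two baseline contrasts

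*Combined protocol and SAP*

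**What the plan says.** Section 4.2 defines the motor endpoint (UPDRS III in PD, with the ET scale given as "tremor rating scale for ET subjects at 3- and 6-month follow-up visits compared to baseline") and the quality-of-life endpoint (PDQ-39 in PD, and "QUEST for ET subjects at the 3- and 6-month follow-up visits compared to baseline"). Both are changes against baseline, and Appendix IX repeats them. The hypotheses in section 8.1.2 use the same reference, for example "The Informity tool will identify DBS parameters that improve motor symptom scores compared to baseline".

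For the analysis, section 8.1.2 states that "a repeated measure analysis of variance (RMANOVA) will be conducted to determine statistical differences from baseline", and then that "Post-hoc Tukey's pairwise comparisons will follow to determine specific differences between follow-up visits". Section 8.4 adds "Family-wise error for RMANOVA will be addressed using Tukey's pairwise post-hoc comparisons" and "All statistical tests will be performed with a type-1 error rate 0.05, unless otherwise stated".

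Section 8 does not name the ANOVA error term. It gives no sphericity test, epsilon correction or covariance structure, and it does not say whether tests are one- or two-sided.

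**The concern.** Two separate issues arise.

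The first is a mismatch between endpoint and test. Each endpoint needs two contrasts against one reference, but Tukey on three visits protects three pairs. The third pair, 3 versus 6 months, answers no stated question and raises the bar for the two that do. The two endpoint contrasts are never named as the planned tests, and an omnibus F test cannot say which visit differs from baseline.

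The second is the standard error. A classical repeated-measures ANOVA followed by Tukey uses one pooled subject-by-visit error for every pair. That is right only if all three between-visit differences have the same variance. Here baseline is measured under omnidirectional stimulation and both follow-ups come after programming with the tool, so equal variances cannot be taken for granted. If they are unequal, the standard errors of the endpoint contrasts are wrong.

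The scales differ by diagnosis, so each analysis has at most 20 subjects. Quality of life may have fewer, because section 6.1.1 allows the baseline questionnaire to be skipped in some cases and section 8.5 rules out imputation.

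**Working it through.** The documents give no power, effect size, SD or correlation for these endpoints, so there is no stated figure to reproduce. The effect size and correlations below are assumptions.

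**Inputs.** n = 20 per diagnosis (section 3.0), 3 visits, alpha 0.05 (section 8.4). Tests are assumed two-sided. The true change is assumed to be dz = 0.65 SD of the difference at both visits.

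**Step 1: critical values.**
- Pooled error df = (20 − 1)(3 − 1) = 38; paired-contrast df = 20 − 1 = 19.
- Tukey: q(0.95; 3, 38)/√2 = 3.449/1.414 = 2.439, or 0.0195 per comparison.
- Dunnett, two contrasts, pooled error (38 df): 2.30.
- Dunnett, contrast-specific error (19 df): 2.39.
- Bonferroni for two, paired t (19 df): 2.433.

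**Step 2: power per baseline contrast if sphericity holds.** The noncentrality is 0.65 × √20 = 2.907. The noncentral t gives:
- Tukey 68.0%
- pooled Dunnett 72.7%
- Dunnett on 19 df 69.6%
- Bonferroni paired t 68.1%
- Holm paired t, by simulation, about 74%

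At other effect sizes, Tukey against pooled Dunnett is 42.9% vs 48.2% (dz 0.5) and 86.7% vs 89.5% (dz 0.8).

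**Step 3: what a pooled error does if sphericity fails.** With unit variances, each difference has variance 2(1 − ρ), and the pooled term estimates the average of the three. Correlations are listed as baseline–3 months / baseline–6 months / 3–6 months.
- 0.5/0.5/0.8: variances 1.0, 1.0, 0.4; average 0.8. The baseline SE is multiplied by √(0.8/1.0) = 0.89, so it is too small.
- 0.4/0.4/0.9: variances 1.2, 1.2, 0.2; average 0.867. The factor is √(0.867/1.2) = 0.85, so it is too small.
- 0.8/0.8/0.5: variances 0.4, 0.4, 1.0; average 0.6. The factor is √(0.6/0.4) = 1.22, so it is too large.

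**Step 4: simulation at n = 20.** Ranges span runs of 40,000 and 200,000 trials. The false-finding columns give the chance of at least one false baseline contrast when nothing changes. Power is per contrast at dz = 0.65.

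| Correlations | False finding, pooled Tukey | False finding, pooled Dunnett | False finding, Holm paired | Power, Tukey | Power, Holm |
|---|---|---|---|---|---|
| 0.6/0.6/0.6 | 3.6–3.7% | 4.9–5.1% | 4.6–4.8% | 68% | 74% |
| 0.5/0.5/0.8 | 5.8–5.9% | 7.5–7.6% | 4.2% | 76% | 73% |
| 0.4/0.4/0.9 | 6.5–6.7% | 8.3–8.4% | 3.5–3.6% | 79% | 72–73% |
| 0.8/0.8/0.5 | 1.2% | 1.7–1.8% | 4.8–4.9% | 48% | 76% |

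In rows 2 and 3 Tukey's higher power comes from an error rate above 5%. Holm with contrast-specific errors stays below 5% in every row.

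**The case against.** Tukey is not invalid. When its assumptions hold it controls family-wise error and is merely conservative for two contrasts. Section 8.1.2 gives differences between follow-up visits as its purpose, and section 6.3.1 allows re-programming at follow-up, so a 3- versus 6-month comparison has some clinical interest. That stands as a reason to report the comparison. It does not make it an endpoint, and it is no reason to let it share the error budget of the endpoints.

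The pooled error is an inference. The plan is silent, and section 8.0 says further detail may sit in a separate SAP. If that SAP specifies contrast-specific errors, the sphericity half of this point falls away.

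A reader might infer that pooling itself costs power for the baseline comparisons. That does not hold in general. Under sphericity pooling doubles the degrees of freedom, and Tukey then matches the Bonferroni paired t (68.0% vs 68.1%). When sphericity fails the effect goes either way.

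A reader might also assume that both follow-ups are under the same settings and treat the inflated-error rows as the expected case. Section 6.2.1 expects the configuration to be kept only until the 3-month visit, and section 6.3.1 allows changes there and recognises routine programming between visits. The correlation pattern is therefore unknown.

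Finally, the 4- to 5-point gain of pooled Dunnett over Tukey at dz 0.65 should not be credited to a contrast-specific analysis. Dunnett on 19 df gains only 1 to 2 points.

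**Conclusion.** The mismatch is in the text: two baseline contrasts are the endpoints, and the adjustment covers three pairs. At n = 20, dz = 0.65 and sphericity, this means about 68% power per contrast with Tukey against about 74% with Holm. Holm's gain depends on a real change at both visits. If only one visit changes, its power is close to the Bonferroni figure of 68.1%, which is no gain over Tukey.

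The missing specification of the error term is also in the text, but its consequence is conditional. If a pooled error is used, the chance of any false baseline finding is about 5.9% to 6.7% in the two patterns where the follow-ups correlate more with each other than with baseline. In the reverse pattern power is about 48% against 76%. The documents do not say which pattern applies.

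The importance is low. These are secondary endpoints in a single-arm post-market study with no stated power, and the primary endpoints are not touched.

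**What to change.** In sections 8.1.2 and 8.4, replace the Tukey step with two planned contrasts for each endpoint: 3 months versus baseline and 6 months versus baseline. Run them within each diagnosis on its own scale. Give each contrast its own standard error, from paired differences or from a repeated-measures model with unstructured covariance, and adjust the pair by Holm. State whether the tests are two-sided. Report 3 versus 6 months as an estimate with a confidence interval, without a formal test.

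Do not simply substitute Dunnett on the pooled error. Where the follow-ups correlate more with each other than with baseline, that raises the chance of any false baseline finding to about 7.5% to 8.4%.

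The cost is wording only, with no change to visits or data. Two things are given up: 3 versus 6 months is no longer formally tested, and contrast-specific errors have about 19 rather than 38 degrees of freedom.

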### 8.2 Timing of Analysis

The dataset will be frozen for analysis when all subjects have completed the 6-month follow-up visit and have evaluable primary endpoint data at the 6-month follow-up visit.

### 8.3 Subgroup Analysis

Subgroup analysis will be performed on the basis of diagnosis (Parkinson's disease or essential tremor). Subgroup analysis will also be performed for those subjects who were programmed with DBS contact 2 or 3 (full ring or individual segments) as a cathode at the Baseline visit.

### 8.4 Multiplicity

All statistical tests will be performed with a type-1 error rate 0.05, unless otherwise stated. Family-wise error for RMANOVA will be addressed using Tukey's pairwise post-hoc comparisons.

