The full benefits of dDBS are only realized if the stimulation parameters are selected appropriately to focus the VTA within the targeted brain area and avoid non-targeted brain regions. The Infirmity tool, available within the Clinician Programmer iPad application (Artemis version 3.7 or later), provides a standardized workflow to guide clinicians or trained healthcare providers through the DBS monopolar review screening process. This process involves assessment of the stimulation amplitudes that produce partial or complete therapeutic benefits and transient or sustained side effects, and is performed by individually testing each of the different electrodes on the dDBS lead. The Infirmity tool enables the neurologist to simultaneously perform this testing on a patient and record the results (Figure 3). Moreover, the tool allows the neurologist to review the results in different formats to aid in the selection of the best contact configuration for that patient (Figure 4). The selection of the best contact configuration is made on the basis of maximizing the width of the therapeutic window and minimizing stimulation power (total electrical energy delivered [TEED]).

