## 4.0 ENDPOINTS

### 4.1 Primary Endpoints and Rationale

- 1) Change in therapeutic window size at the Informity programming visit compared to baseline
- 2) Change in TEED at the Informity programming visit compared to baseline

The primary endpoints were selected because it is hypothesized that they will be significantly improved following Infinity tool programming. Specifically, it is hypothesized that therapeutic window size will increase and TEED will decrease at the Informity programming visit compared to baseline.

*This confidential document is the property of Abbott and shall not be reproduced, distributed, disclosed or used without the express written consent of Abbott*

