### 8.1 Statistical Analyses

#### 8.1.1 Primary Effectiveness Endpoint Analyses

The hypotheses for the primary endpoints are that the Informity tool will identify DBS parameters that:

1. Have a larger therapeutic window size compared to programmed parameters at baseline
2. Have a lower TEED compared to programmed parameters at baseline

A comparison of therapeutic window and TEED will be performed for the contact configuration used at baseline, and the contact configuration used after Informity programming with the Informity tool, using a paired t-test. All statistical analyses will be conducted assuming a type-1 error rate of 0.05 unless specifically stated otherwise. The change in TEED from baseline to Informity programming will be used to calculate a corresponding battery longevity projection.

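### Do the two primary tests, each at 0.05 with no stated sidedness or one-or-both rule, need a multiplicity adjustment?

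*Combined protocol and SAP*

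**What the plan says.** Section 4.1 names two primary endpoints, the changes in therapeutic window size and in TEED from baseline to the Informity programming visit. It gives a direction for each: "it is hypothesized that therapeutic window size will increase and TEED will decrease at the Informity programming visit compared to baseline". It also says of the pair that "it is hypothesized that they will be significantly improved following Infinity tool programming".

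Section 8.1.1 turns these into two numbered hypotheses about the settings the tool will find: "Have a larger therapeutic window size compared to programmed parameters at baseline" and "Have a lower TEED compared to programmed parameters at baseline". Each is examined by paired t-test, with the general statement "All statistical analyses will be conducted assuming a type-1 error rate of 0.05 unless specifically stated otherwise".

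Section 8.4, headed Multiplicity, repeats that rate ("All statistical tests will be performed with a type-1 error rate 0.05, unless otherwise stated") and adds one method: "Family-wise error for RMANOVA will be addressed using" Tukey's pairwise comparisons. Under section 8.1.2 the repeated-measures analysis serves the motor-score and quality-of-life endpoints, which are secondary.

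No section says whether the primary tests are one- or two-sided, or whether one or both hypotheses must be supported. Section 8.0 allows further detail in a separate SAP, but the topics it lists do not include multiplicity, sidedness or a decision rule. Section 2.1.1 gives the objective as characterising performance. No section defines study success, and section 8.7 sets no statistical criterion for termination.

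**The concern.** A plan with two primary endpoints, directional hypotheses and a multiplicity section would normally say how the two tests combine. This one addresses family-wise error for secondary comparisons and is silent on the primaries.

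If a favourable result on either endpoint counted as support, there would be two chances of a false one, and the rate could be about twice that of a single test. Unstated sidedness adds another factor of two, because a 0.05 test puts 2.5% in the favourable tail if two-sided and 5% if one-sided. If one endpoint were significant and the other not, the reading could be settled after the data were seen. The primary data are complete at the Informity visit, before the 3-month point at which section 8.6 first allows an interim analysis. At stake is how a significant primary result may be read.

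**Working it through.** **Inputs.** Two primary hypotheses, a paired t-test for each, and 0.05 per test (sections 8.1.1 and 8.4). Up to 40 subjects (section 5.8). The documents give no correlation between the two changes, no effect size and no standard deviation, so any value used for these below is an assumption. The plan states no family-wise rate, so there is no figure of its own to reproduce.

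**Favourable tail per test.** *a* = 0.025 if the 0.05 test is two-sided and *a* = 0.05 if it is one-sided.

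**Either endpoint suffices, neither effect real.** Under independence the chance of at least one favourable result is 1 − (1 − *a*)². Under any dependence it is at most 2*a*.

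- Two-sided: 1 − 0.975² = 0.0494; bound 2 × 0.025 = 0.05.
- One-sided: 1 − 0.95² = 0.0975; bound 2 × 0.05 = 0.10.

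Independence is doubtful, since section 1.1.1 says the choice of configuration is "made on the basis of maximizing the width of the therapeutic window and minimizing stimulation power". For a bivariate normal pair with correlation *r* (positive meaning both favourable), the rate is 2*a* minus the probability that both are favourable:

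| *r* (assumed) | Two-sided 0.05 | One-sided 0.05 |
|---|---|---|
| 0 | 4.9% | 9.75% |
| 0.3 | 4.8% | 9.3% |
| 0.5 | 4.5% | 8.8% |
| 0.9 | 3.5% | 6.8% |

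Simulated paired t-tests (200,000 runs, independent changes, n = 40) give 4.9% and 9.7%, so the normal approximation is adequate.

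**Both endpoints required.** The chance of a false joint claim cannot exceed the rate of the single test whose null is true: at most 2.5% two-sided or 5% one-sided. This limit is reached when one effect is large and the other zero. With neither effect real and *r* = 0 it is *a*²: 0.025² = 0.0006, or 0.05² = 0.0025. There is no inflation.

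**The four readings against the stated 0.05.**

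| | Both required | Either suffices |
|---|---|---|
| Two-sided | at most 2.5% | at most 5% |
| One-sided | at most 5% | up to 10% |

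Only one cell exceeds 5%, and it needs two choices that the plan does not make.

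**What an imposed adjustment would cost.** Holm at an overall two-sided 0.05 requires the smaller p-value to be below 0.025. By the noncentral t distribution at n = 40, the change detectable with 80% power at that step rises from 0.454 to 0.504 SD. Take a true change of 0.454 SD, a benchmark defined by 80% power at n = 40. Power per endpoint then falls from 80% to 76–77% if both effects are real, and to about 71% if only one is. In return, the two-sided false favourable rate falls from 4.9% to about 2.5%.

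**The case for a change.** The strongest case for a change is that sections 4.1 and 8.1.1 state formal hypotheses tested for significance, and that an expectation of improvement on both endpoints is not a rule for a split result. Such a result is quite possible: with a true 0.454 SD change on both endpoints and n = 40, exactly one is significant in about 32% of simulated trials at correlation 0 and 23% at 0.5. A sentence or two would settle the reading, with no new data or visits.

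It stands that the rule is unwritten and that writing it down would be tidier. The rest carries less weight. The doubling is measured against a 2.5% directional standard that appears nowhere in the plan; its only stated rate is 0.05, and two-sided tests keep the favourable rate within it. Section 8.1.1 can also be read as complete endpoint by endpoint, with two numbered hypotheses, one test each and one error rate. A split result is then reported as one hypothesis supported and one not. There is no overall primary hypothesis left undecided.

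The candidate remedies also point in opposite directions. A joint rule would allow no primary claim from one endpoint alone, while Holm would allow it at a stricter first threshold. Choosing between them depends on the claim the sponsor intends, and nothing in the plan shows that either is needed.

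Finally, all these rates assume that the mean change is zero when the tool has no real benefit. Section 6.2.1 has several configurations tested and one selected with the help of ranked results, which could favour the selected setting even without true differences. That is a separate question, and splitting alpha between the two endpoints would not address it.

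**Conclusion.** The observation is accurate: sidedness and a one-or-both rule are not written for the two primary tests. It does not call for a change to the plan. The wording leans towards both improvements being expected, and under that reading there is no inflation. With two-sided tests, the usual default, the false favourable rate is at most 5% even if either endpoint suffices. It passes 5% only if the tests are one-sided and either endpoint suffices (9.75% under independence, at most 10%).

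Analysts can fill the gap sensibly by running both paired t-tests two-sided at 0.05, reporting both results whatever they show, and drawing a joint conclusion only if both are significant in the hypothesised direction. That contradicts nothing in the plan. Formal family-wise control in a single-arm characterisation study with no success criterion is a fair trade-off that statisticians would debate, since it could lower power per endpoint from 80% to as little as about 71% at the benchmark effect. The conclusion rests on the either-or-both and sidedness cases set out above; the correlations and the 0.454 SD benchmark are assumptions, but the 5% and 10% bounds hold under any dependence.

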### 8.5 Procedures for Accounting for Missing Data

Missing data will be reported at each visit for each outcome. No imputations will be performed for missing data. If the session log data for the programming session prior to enrollment is missing or corrupted for a given subject, then this subject will not be included in the statistical analysis for the time required for programming.

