## 3.0 CLINICAL STUDY DESIGN

This is a prospective, non-randomized, single-arm, multi-center, post-market clinical study designed to evaluate Abbott's Informity tool for Infinity DBS systems.

This clinical study will be conducted at up to 5 centers in the United States.

[figure not shown]
Up to 40 patients will be enrolled in the study. Of these subjects, up to 20 will have PD and up to 20 will have ET. All patients will have received DBS systems prior to enrolling in the study.

The primary and secondary endpoints will be evaluated when all subjects have completed their 6-month follow-up visit.

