### Lost-to-Follow-up

If the subject misses two consecutive scheduled follow-up time points and the attempts at contacting the subject detailed below are unsuccessful, then the subject is considered lost-to-follow-up. Site personnel shall make all reasonable efforts to locate and communicate with the subject (and document these efforts in the source documents), including the following, at each contact time point:

- A minimum of two telephone calls on different days over the specified follow-up windows to contact the subject should be recorded in the source documentation, including date, time and initials of site personnel trying to make contact.
- If these attempts are unsuccessful, a certified letter should be sent to the subject.
- If a subject misses one or more non-consecutive follow-up contact time points, it will be considered a missed visit. The subject may then return for subsequent visits. If the subject misses two consecutive time points and the above-mentioned attempts at communicating with the subject are unsuccessful, the subject will be considered lost-to-follow-up.

**Note:** Telephone contact with general practitioner, non-clinical investigation neurologist or relative without the presence of the subject or indirect documentation obtained via discharge letters will not be considered as subject contact.

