### 6.3 Follow-up Assessments

#### 6.3.1 Follow-up for All Subjects (Site Visit)

Follow-up visits are scheduled at 3 and 6 months after the Infirmity Programming visit. If Infirmity Programming is performed over back-to-back days, then follow-up visit timing is based on the date of the second day of programming.

At each visit, the following procedures and assessments must be completed:

- Quality of life assessment
- Motor symptom evaluation (stimulation ON/medication ON) performed by a blinded assessor
- Medication (only PD or ET medications)- indicate the drug category the subject is currently taking on a long-term basis, i.e. no short-term medication
- Interrogation of programmed settings and program impedance.

The quality of life assessment must be performed prior to the motor symptom evaluation. Motor symptom evaluation will be performed by a blinded assessor, who will not be aware of the subject's programming.

If in the Investigator's opinion, the selected DBS electrode contact configuration does not provide adequate therapy for the subject at a follow-up visit, the subject's DBS system parameters can be adjusted. by re-programming with the Infirmity tool. This re-programming should be performed using the same procedure detailed in Section 6.2.1, and by the same programmer who programmed the patient during the Infirmity Programming visit. If re-programming is performed, motor symptom evaluation must be performed before and after re-programming at the follow-up visit.

An unscheduled visit is defined as any visit that occurs outside of a specified study visit related to an adverse event or withdrawal of the patient from the study. Any routine programming that occurs outside of a study visit will be captured at the subsequent study visit. Any unscheduled visit needs to be documented by completing the Unscheduled Visit form and other appropriate forms if applicable (Adverse Event, Withdrawal, Programming, and Medication).

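### As conventionally run, the RMANOVA drops a subject from an outcome's whole analysis when one of its three scores is missing; a mixed model on all observed scores would not

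*Combined protocol and SAP*

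**What the plan says.** For motor scores, section 8.1.2 states that "a repeated measure analysis of variance (RMANOVA) will be conducted to determine statistical differences from baseline". For QoL it states that "The change in quality of life measurement will also be analyzed using a RMANOVA followed by Tukey's pairwise comparisons". There are three measurement occasions: baseline (section 6.1.1) and two follow-ups, since "Follow-up visits are scheduled at 3 and 6 months after the Infirmity Programming visit" (section 6.3.1).

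On missing data, section 8.5 has missingness reported by visit and outcome, and then says "No imputations will be performed for missing data". Its one explicit exclusion rule covers lost session logs, where "this subject will not be included in the statistical analysis for the time required for programming". It has no matching rule for motor or QoL scores.

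Several provisions make incomplete subjects likely:

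- Section 5.5, on loss to follow-up: "If a subject misses one or more non-consecutive follow-up contact time points, it will be considered a missed visit". Such a subject may attend later visits.
- Section 5.5 also says that withdrawn subjects are neither replaced nor followed further.
- Section 6.1.1 waives baseline QoL in two cases: when baseline falls on the enrollment day, and when the subject was switched to omnidirectional stimulation on the day of the Baseline visit.

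The samples are small: "Of these subjects, up to 20 will have PD and up to 20 will have ET" (section 3.0). Each diagnosis has its own motor and QoL scale (section 4.2).

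**The concern.** Classical RMANOVA works on one complete row per subject. Where nothing is imputed and no other rule is given, the usual result is that a subject with a gap is removed. A subject scored at baseline and Month 3 but not at Month 6 then contributes nothing to the Month 3 contrast, although both of its scores were observed. The same holds with the months reversed. A subject whose baseline QoL was waived is lost even from the comparison of Month 3 with Month 6.

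Two things are at stake for secondary endpoints 1 and 2. The first is precision, with at most 20 subjects per scale. The second is the group being described: the Month 3 effect would be estimated only in people who also have a Month 6 score. If subjects who respond poorly are likelier to be missing later, the estimate is too favourable even at a visit where they were measured. The withdrawal reasons in section 5.5 include system revision, explant and participation ceasing to be medically appropriate, so a link with poor response is plausible, though not shown.

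**Working it through.** The plan gives no power target, effect size, SD or missed-visit rate for these endpoints, so it has no figure to reproduce. The inputs taken from it are 20 subjects per scale (section 3.0), three occasions (sections 6.1.1 and 6.3.1) and a type-1 error of 0.05 (section 8.1.2), here taken as two-sided. All other inputs are assumptions.

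**1. Does RMANOVA drop incomplete subjects?** In a simulated dataset of 20 subjects, four lacked one follow-up score each (two at Month 3, two at Month 6).

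- A standard routine (AnovaRM in statsmodels) rejected the data as unbalanced. It ran only after the four were removed, on 16 subjects, although each baseline-to-follow-up contrast had 18 observed pairs.
- A mixed model used all 20 subjects and 3 × 20 − 4 = 56 scores.

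**2. Subjects retained.** Let m be the chance of a missing score at each follow-up, independent between visits, with baseline observed. Complete subjects = 20(1 − m)²; usable pairs per contrast = 20(1 − m).

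| m | Complete | Pairs per contrast |
|---|---|---|
| 5% | 18.1 | 19.0 |
| 10% | 16.2 | 18.0 |
| 15% | 14.4 | 17.0 |
| 20% | 12.8 | 16.0 |

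**3. Power.** For a paired t-test (noncentral t) and an assumed change of 0.6 SD of the change, power is 67% at n = 18, 61% at n = 16 and 51% at n = 13. Rounding complete subjects to whole numbers, the loss is 67% to 61% at m = 10%, and 61% to 51% at m = 20%. This approximates the RMANOVA contrast, which uses a pooled error term.

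**4. Waived baseline QoL.** If a share w has no baseline QoL and m = 10%, complete subjects = 20(1 − w)(0.9)². This gives 14.6, 12.2 and 8.1 for w = 10%, 25% and 50%.

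**5. Missing completely at random.** In 1,500 simulated trials (n = 20, m = 10%, true change −0.50), completers averaged −0.495 (SD 0.253) and available pairs −0.498 (SD 0.238). There is no bias; the variance ratio is (0.253/0.238)² = 1.13.

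**6. Missing Month 6 depends on Month 3.** Assume changes with unit SD, a true change of −0.40 at both visits (negative is improvement) and a correlation of 0.6 between the two changes. Let z be the deviation of a subject's Month 3 change from its mean, with logit P(Month 6 missing) = a + s·z and a set to give the stated missing rate. Let δ be the mean of z among those retained, found by numerical integration. Completers then show −0.40 + δ at Month 3 and −0.40 + 0.6δ at Month 6.

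| s | Missing | δ | Month 3 | Month 6 |
|---|---|---|---|---|
| 1 | 10% | −0.091 | −0.49 | −0.45 |
| 1 | 20% | −0.173 | −0.57 | −0.50 |
| 2 | 10% | −0.143 | −0.54 | −0.49 |
| 2 | 20% | −0.262 | −0.66 | −0.56 |

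A likelihood analysis of all observed scores recovers −0.40 here, as it should, because the data were generated missing at random. A separate simulation at n = 20 agrees in direction: with about 22% missing at Month 6 and a true Month 3 change of −0.50, completers gave −0.61 and available pairs −0.51.

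**The case against.** The strongest reply is that the documents never say complete-case or listwise. Section 8.1.2 names a family of analyses, not an estimator or a program, and a fit with subject as a block or random effect would keep incomplete subjects. That stands as a limit. A reader might infer that the plan prescribes deletion; it does not. Deletion follows from the conventional way of running the named method when nothing else is specified.

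A reader might also infer that one gap removes a subject from both the motor and the QoL results. The documents do not support that, because these are separate analyses. A wholly missed visit affects both; a single missing questionnaire affects only its own outcome.

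Nor is the no-imputation sentence itself the fault. It is compatible with a sound analysis; the weakness lies in the method named in section 8.1.2.

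The plan has some partial protection. Section 5.5 asks sites to attempt a final visit before withdrawal, with blinded motor and QoL assessments, so some leavers would be measured. No rule says which occasion that score represents. Section 8.0 allows a separate SAP to hold sensitivity analyses, but only as an option. Section 8.2 ties the data freeze to completion of Month 6, which does not restore a missed Month 3 score or a waived baseline.

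Finally, the bias figures depend wholly on assumed missingness. The documents give no reason to prefer those values, and under missing completely at random there is no bias. That is correct, and the figures are illustrations only.

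**Conclusion.** The point holds for RMANOVA as conventionally run: for each outcome, observed scores from subjects with one gap would be discarded, and the plan's own visit, withdrawal and waiver rules make such gaps likely. At an assumed 10% to 20% missing per follow-up, the cost is about 2 to 3 of 20 subjects per contrast (18 − 16.2 = 1.8; 16 − 12.8 = 3.2), and more for QoL if many baselines are waived. Bias arises only if missingness relates to response. Under the assumptions in step 6, a true −0.40 SD would appear as about −0.49 to −0.66 SD at Month 3 and −0.45 to −0.56 SD at Month 6.

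A reader might infer that the study's main conclusions are at risk. They are not: the primary endpoints use paired t-tests on baseline and the programming visit (section 8.1.1) and are untouched. The change should be made because it improves secondary endpoints 1 and 2 at little cost.

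**What to change.** In section 8.1.2, replace RMANOVA for motor and QoL scores by a linear mixed model for repeated measures, as follows:

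- Fit by REML to all observed scores, separately for PD and ET because the scales differ.
- Use visit as a fixed factor, an unstructured within-subject covariance and Kenward-Roger degrees of freedom.
- Prespecify two contrasts: 3 months minus baseline and 6 months minus baseline. Align section 8.4, which ties error control to RMANOVA and Tukey.
- Keep the no-imputation sentence in section 8.5, and report the completers-only result as a sensitivity analysis.
- State how subjects with waived baseline QoL are handled. Their follow-up scores contribute under missing at random but give no observed change from baseline, so add a sensitivity analysis restricted to subjects with observed baseline QoL.
- Say whether, and at which occasion, a final pre-withdrawal assessment enters the model.

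The cost is a few sentences of plan text and slightly more analysis work, with no new data. The main analysis then relies on missing at random, which is weaker than what completers-only results need but cannot be verified from the data.
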